4.1.2 Selection of doses in the trial and dose modifications

This trial, 1368-0007, aims to offer a maintenance treatment for patients with perianal CD who have failed available therapies and whom are considered to have benefited from previous induction therapy in the parent trial.

The spesolimab subcutaneous dose regimen chosen for 1368-0007 has thus been selected with the objective of achieving maintenance of induction therapy effect with the safest profile based on available data from Phase I and Phase II studies in HV and patients with PPP and UC, respectively.

Bioavailability of the s.c. relative to the i.v. formulation of spesolimab is approx. 50%-70 % (cf. section 6.2 of IB [c03320877-08](#)). A subcutaneous dose of 300mg would therefore correspond to ~210 mg as an i.v. dose and thus represents the lowest dose of 3 mg/kg which was found to be fully active in the indirect target engagement assays in studies 1368-0001 and 1368-0002.

The dosing interval of every 4 weeks (q4w) was selected based on the half-life of approximately 4-5 weeks in healthy volunteers and PPP patients, as determined in the PoCC trial 1368-0015 and phase I studies 1368-0001 and 1368-0002, respectively. Thus, after one half life (~4 weeks) patients' exposure would drop below the threshold required to maintain maximal target engagement.

In patients experiencing a fistula relapse, a single 1200mg i.v. high treatment dose will be administered, followed by a maintenance dose of 600mg q4w, as defined in [Section 3.1](#) to double the exposure compared to the original failing maintenance regimen.

The loading i.v. dose of 1200mg is expected to be at the plateau of the dose/response curve and to provide maximal efficacy based on data indicating high and sustained target engagement at doses ≥ 3 mg/kg and a half-life as long as 4-5 weeks in healthy volunteers and PPP patients respectively (cf. sections 6.1 and 6.2 of the IB [c03320877-08](#)). This dosing regimen will achieve exposures below the highest dose regimen that was found safe in phase I studies. It therefore is also being tested in ongoing studies in IBD trials. These doses may be adapted later (via protocol amendment) based on emerging data from other trials with spesolimab.

4.1.3 Method of assigning patients to treatment groups

Not applicable, as all patients in this trial will receive the same treatment.

4.1.4 Drug assignment and administration of doses for each patient

During visit M1, eligibility criteria will be assessed and eligible patients will be allocated to receive open-label active treatment. The assignment of treatment will be done via Interactive Response Technology (IRT). The appropriate medication number will be assigned and documented in the CRF.

Injection site should not be close to a vein and it should avoid sites where the skin is tender, bruised, erythematous, or indurated, and should be alternated to other areas for subsequent doses.

Detailed instructions for Handling and Use of s.c. injection are provided in the ISF.

Patients must be closely monitored for local or systemic hypersensitivity reactions for 1 hour following s.c. study drug administration. Subcutaneous administration of biologic agents involves the risk of local (injection site) or systemic hypersensitivity reactions. Study personnel should observe the injection site for signs of redness, swelling or hardness. They should also ask patients about itching, dizziness, or shortness of breath. Patients should be advised that if they experience redness, swelling, or other changes at the injection site, they should notify site personnel. They should further be advised that if they experience itching all over, or a feeling of being swollen, dizzy, or short of breath, they should seek emergency medical attention immediately and notify site personnel.

A single dose of 1200 mg spesolimab i.v. will be used as fistula relapse treatment. Intravenous infusion including observational time for possible infusion reactions will last approximately 2.5 hours.

Detailed instructions for the preparation of the i.v. infusion solution, the volume to be administered and the infusion rate are provided in the ISF.

During the COVID-19 pandemic, physical visits to the sites may need to be restricted to ensure patient safety. Based on a thorough assessment of the benefits and risks, the investigator may discuss with BI to continue the trial treatment and trial medication may be shipped to the patient's home if acceptable according to local law and regulations.

In case of safety concerns, e.g. due to infusion reactions, it is in the discretion of the investigator or his/her designee to adapt the infusion scheme (cf. [Section 4.2.1](#) for handling of infusion reactions). Detailed instructions for handling of infusion reactions are also provided in the ISF.

The administration of the trial medication intravenously on all applicable study days will be done under supervision of the investigating physician or a designee at the site. If available, a pharmacist should prepare the study medication. The four eye principle (two-person rule) should be applied for preparation (e.g. choosing the correct vials with the correct medication number) and administration of trial medication.

Dose modifications or adjustments are not permitted. In exceptional cases of missed or delayed visits, if any of these visits has to be rescheduled, the date of subsequent visit should be calculated from Day 1 of maintenance treatment or if the patient is on fistula relapse treatment from the first s.c. drug administration after the last fistula relapse. There should be at least 14 days between two consecutive study drug administrations.

4.1.5 Blinding and procedures for unblinding

This is an open label, single arm trial; therefore, no blinding will be necessary. In this open-label trial, treatment allocation will not be concealed throughout the trial.

4.1.6 Packaging, labelling, and re-supply

The investigational medicinal products will be provided by BI or a designated CRO. They will be packaged and labelled in accordance with the principles of Good Manufacturing Practice (GMP). Re-supply to the sites will be managed via an IRT system, which will also monitor expiry dates of supplies available at the sites.

For details of packaging and the description of the label, refer to the ISF.

4.1.7 Storage conditions

Drug supplies will be kept in their original packaging and in a secure limited access storage area according to the recommended storage conditions on the medication label. A temperature log must be maintained for documentation.

If the storage conditions are found to be outside the specified range, the Clinical Research Associate (CRA), as provided in the list of contacts, must be contacted immediately.

4.1.8 Drug accountability

The investigator or designee will receive the investigational drugs delivered by the sponsor when the following requirements are fulfilled:

- Approval of the clinical trial protocol by the IRB / ethics committee
- Availability of a signed and dated clinical trial contract between the sponsor and the investigational site
- Approval/notification of the regulatory authority, e.g. competent authority
- Availability of the curriculum vitae of the Principal Investigator
- Availability of a signed and dated clinical trial protocol
- Availability of the proof of a medical license for the Principal Investigator
- Availability of FDA Form 1572 (if applicable)

Investigational drugs are not allowed to be used outside the context of this protocol. They must not be forwarded to other investigators or clinics. Patients should be instructed to return unused investigational drug.

The investigator or designee must maintain records of the product's delivery to the trial site, the inventory at the site, the use by each patient, and the return to the sponsor or warehouse / drug distribution centre or alternative disposal of unused products. If applicable, the sponsor or warehouse / drug distribution centre will maintain records of the disposal.

These records will include dates, quantities, batch / serial numbers, expiry ('use- by') dates, and the unique code numbers assigned to the investigational medicinal product and trial patients. The investigator or designee will maintain records that document adequately that the patients were provided the doses specified by the Clinical Trial Protocol (CTP) and reconcile all investigational medicinal products received from the sponsor. At the time of return to the

sponsor <and/or> appointed CRO, the investigator or designee must verify that all unused or partially used drug supplies have been returned by the clinical trial patient and that no remaining supplies are in the investigator's possession.

4.2 OTHER TREATMENTS, EMERGENCY PROCEDURES, RESTRICTIONS

4.2.1 Other treatments and emergency procedures

4.2.1.1 Allowed concomitant therapies

CD-Related Treatments

Patients in this trial may be on conventional immunosuppressants or anti-TNF α biologic treatment for CD. These may consist of one or more of the following drugs (cf. [Section 4.2.1.2](#)

for restrictions), which are therefore permitted concomitant medications:

- Oral 5-ASA compounds, provided that dose has been stable prior to randomisation in parent trial and during current trial, and/or
- Oral corticosteroids (≤ 20 mg per day of prednisone or equivalent), provided that dose has been stable prior to randomisation in parent trial and during current trial, and/or
- Oral budesonide (≤ 9 mg per day), provided that dose has been stable in parent trial and during current trial, and/or
- Azathioprine, 6-MP, 6-TG or methotrexate, provided that dose has been stable in parent trial and during current trial,
- Approved anti-TNF α (e.g. infliximab, adalimumab, certolizumab pegol; or respective biosimilars) provided that dose has been stable in parent trial and during current trial
- Probiotics (e.g. *S. boulardii*) provided that dose has been stable for > 4 weeks prior to randomisation
- Regular use of anti-diarrheals

Dose has to be stable before rolling over and throughout the trial. The only exceptions are anti-diarrheals, which may be adjusted to current symptoms, and steroid reduction.

Patients who present a luminal flare (but no fistula relapse) might receive standard of care treatment for moderate-to-severe CD, while continuing with their spesolimab maintenance dose. Thus, on top of the concomitant therapies listed above, patients with luminal flare (but no fistula relapse) are also allowed to receive concomitant approved doses for treatment of moderate to severe CD including (but not limited to) the following therapies:

- anti-TNF α (this might be associated to Azathioprine / 6-MP/ MTX)
- Integrin receptor antagonists
- IL12/ 23 antagonists

Steroids

Systemic steroids dosed intravenously or orally for less than 24 hours as treatment of infusion or anaphylactic reactions are permitted and do not lead to treatment discontinuation (see [Table 4.2.1.2:1](#)).

If mild-to-moderate infusion or anaphylactic reaction had already occurred in the same patient in the parent trial or occurs in this trial, the patient may be pre-treated with steroids as secondary prophylaxis before future future IMP administrations.

Locally administered steroids as e.g. intraarticular, nasal inhalation or intraocular administration are allowed, but their application has to be carefully monitored and reported in CRF

Peri-OP antibiotics

Peri-OP antibiotics are allowed if required according to standard of care.

Other treatments

Stable doses of concomitant therapies for chronic conditions, for which neither the condition nor the treatment are judged to exclude the patient from participation are permissible. All concomitant medications should be carefully evaluated by the investigator and the sponsor representative should be contacted when there are questions regarding concomitant medications.

Management of Adverse Events:

“Systemic hypersensitivity including infusion reaction and anaphylactic reaction”

In case of infusion reactions / systemic hypersensitivity including anaphylactic reaction emerging during or after infusion / injection(s) of trial medication, the investigator should consider in accordance with severity of the reaction and local standard of care to:

- Immediately interrupt the infusion / Stop further injections
- Treat with systemic anti-histamines, i.v. steroids, and in case of a severe allergic reaction (eg, anaphylactic reaction) epinephrine
- Draw a plasma sample for IgE and ADA as detailed in the Lab Manual (ISF)
- Consider the evaluation of histamine, serum tryptase, and complement components

In case of infusion reaction /systemic hypersensitivity, based on patient's clinical course and medical judgment, the infusion may be re-initiated / the injection(s) may be continued in case of mild or moderate infusion reactions / systemic hypersensitivity (according to RCTC grading in ISF) at lower speed with gradual increase to complete the infusion / injections as detailed in the Instructions for Preparation and Handling of spesolimab in the Investigator Site File. In any case, the total duration of infusion should not exceed 90 minutes (1.5 hours) provided that the maximum time between the start of preparation and completion of administration of the solution to the patient does not exceed 150 minutes (2.5 hours).

In case of anaphylactic reaction based on the criteria discussed in the statement paper from Sampson HA ([R11-4890](#)) suspected to be caused by the trial medication, the investigator should permanently discontinue treatment with the spesolimab.

When a non-acute hypersensitivity reaction related to immune complexes (i.e., serum sickness) is suspected, a sample for the laboratory assessment for circulating immune complexes (referring to Lab manual) will be taken.

Severe infections (according to RCTC grading in the ISF), serious infections, opportunistic or mycobacterium tuberculosis infection

Treatment of the infection should be initiated promptly according to local standard of care. No further trial medication should be administered until the active infection has resolved. Treatment with spesolimab may be restarted when the patient has recovered according to investigator's assessment.

Latent TB must be treated according to local guidelines. Patient can continue the treatment.

Malignancies

In case of occurrence of malignant neoplasm other than appropriately treated basal cell carcinoma or squamous cell carcinoma of the skin or in situ carcinoma of uterine cervix, the investigator should discontinue treatment with study drug. Diagnostics and treatment have to be initiated according to local standard of care.

4.2.1.2 Restricted medications

Restrictions regarding previous and concomitant treatment are summarized in the following

Table 4.2.1.2:1 Restrictions regarding concomitant treatment

Medication or class of medications	Restriction
Any biologic or non-biologic drug approved for CD other than the anti TNF α listed in section 4.2.1.1	
Not allowed until end of the trial *
 
Approved doses for treatment of moderate-to-severe CD are allowed for rescue medication ONLY in patients who present with luminal inflammatory flare BUT NO FISTULA RELAPSE.

Any investigational or non-approved biologic or non-biologic for CD	Not allowed until end of the trial
Autologous or allogeneic haematopoietic (HSC) or mesenchymal stem cell (MSC) therapy	Not allowed until end of the trial
5-ASA	
Oral administration:
 
Only allowed during the trial, if dose is stable prior to treatment initiation until end of the trial
 
Rectal route of administration:
 
Not allowed from screening up to end of the trial
 
For use as rescue medication, refer to Section 4.2.1.1

Corticosteroids (incl. budesonide)	
Oral administration:
 
Oral systemic corticosteroids only allowed at a dose of \leq 20mg per day of prednisone or equivalent and with stable dose prior to treatment initiation in this study.
 
Oral budesonide (\leq 9 mg per day), provided that dose has been stable prior to treatment initiation in this study.
 
Allowed steroid treatments:
 
Short-term use (<7 days) of systemic (oral or parenteral) corticosteroids is allowed for treatment of AE not related to the underlying CD. Parenteral corticosteroids dosed for less than 24 hours as treatment of infusion or anaphylactic reactions are permitted.
 
Locally administered steroids as e.g. intra-articular, nasal inhalation or intra-ocular administration are allowed.

NSAID	
Chronic use not allowed from screening to end of the trial
 
(Note: occasional use of NSAIDs and acetaminophen for headache, arthritis, myalgias, menstrual cramps, etc., and daily use of baby or low dose (81-162.5mg) aspirin for cardiovascular prophylaxis are permitted.)

Probiotics	Only allowed during the trial provided that dose has been stable prior to treatment initiation and up to end of the trial
Antidiarrheals	Allowed during the trial as needed
Live-attenuated vaccines	Not allowed from screening up to end of the trial
Antibiotics for IBD	Not allowed from screening up to end of the trial (antibiotics given for other indications are allowed if taken for no longer than 3 weeks)

4.2.1.3 Restricted fistula interventions

Surgical interventions for CD are not allowed during the trial.

Any surgical intervention or procedure for perianal and enterocutaneous fistulas (except seton drainage) are also not allowed (patient shall be discontinued) since they would interfere with the clinical endpoints of the trial. Some examples are summarized in [table 4.2.1.3:1](#) (not an exhaustive list).

Table 4.2.1.3:1 Examples of restricted procedures for perianal and enterocutaneous fistulas

Procedure for perianal and enterocutaneous fistulas	Restriction

- Cutting of fistulas- Shortening of fistulas- Splitting of fistulas- Fibrin glue	Not allowed from start of until end of the trial

4.2.2 Other restrictions

4.2.2.1 Restrictions on diet and life style

No restrictions on diet or lifestyle of the patients are required.

4.2.2.2 Contraception requirements

Women of childbearing potential must use highly effective methods of birth control per ICH M3 (R2) that result in a low failure rate of less than 1% per year when used consistently and correctly during the trial, and for a period of at least 16 weeks after the last study drug administration. A double barrier method of contraception is not required. A list of contraception methods meeting these criteria is provided in the patient information.

Female Patients

Acceptable methods of birth control for this trial are:

- Combined (estrogen and progestogen containing) hormonal birth control that prevents ovulation (oral, intravaginal, transdermal)
- Progestogen-only hormonal birth control that prevents ovulation (oral, injectable, implantable)
- Intrauterine device (IUD) or intrauterine hormone-releasing system (IUS)
- Bilateral tubal occlusion
- Vasectomised sexual partner with documented absence of sperm

Or

Patients must abstain from male-female sex. This is defined as being in line with the preferred and usual lifestyle of the patient. Periodic abstinence e.g. calendar, ovulation,

symptothermal, post-ovulation methods; declaration of abstinence for the duration of exposure to study drug; and withdrawal are not acceptable.

Male Patients:

Contraception of male trial participants and female partners of male trial participants are not required.

4.3 TREATMENT COMPLIANCE

Study medication will be administered in accordance with the protocol under supervision of the investigating physician or a designee at the site.

Any missed dose has to be documented and reported to the CTM.

5. ASSESSMENTS

5.1 ASSESSMENT OF EFFICACY

5.2 ASSESSMENT OF SAFETY

Safety will be assessed descriptively based on:

- Adverse events (AEs)
- Serious adverse events (SAEs)
- Clinical laboratory values (haematology, clinical chemistry, coagulation and urinalysis)
- Intensity of adverse events will be assessed by Rheumatology Common Toxicity Criteria (RCTC) version 2.0 (refer to ISF for details)
- Physical examination
- Vital signs
- 12-lead ECG

5.2.1 Physical examination

Complete physical examination will include vital sign assessment and general appearance as well as evaluation of all organ systems. Targeted physical examination will include vital sign assessment and evaluation of organ systems associated with AE(s) symptoms, or extra-intestinal manifestations as well as laboratory abnormalities.

Clinically relevant abnormal findings will be reported as baseline conditions or AEs.

The results must be included in the source documents available at the site.

5.2.2 Vital signs

Vital signs evaluations will be performed at visits as shown in the [Flow Chart](#). This includes body temperature, pulse rate, systolic/diastolic blood pressure and respiratory rate. Respiratory rate, pulse rate, and blood pressure will be measured after patients have been sitting comfortably for at least five minutes. Measurement of vital signs should precede blood sampling to avoid the impact of blood sampling on the vital sign measurements. At dosing visits, vital sign evaluations will be performed pre-dose for both visits with i.v. and s.c. administration of study drug. At s.c. dosing visits, vital signs will be assessed at approximately 10 minutes after study drug administration. Also, at visit M1 and visit M2 (s.c. dosing visits) additional vital signs assessments will be performed approximately 60 minutes post-dose (i.e. 60 min. after last injection). At visits with i.v. dose administration, vital sign evaluations will be performed pre-dose and additional evaluations will be taken at 5 and 60 minutes post-dose

5.2.3 Safety laboratory parameters

Safety laboratory parameters to be assessed are listed in [Table 5.2.3: 1](#). For the sampling time points please see the [flowcharts](#).

All analyses will be performed by a central laboratory; the respective reference ranges will be provided in the ISF.

Patients do not have to be fasted for the blood sampling for the safety laboratory.

Instructions regarding sample collection, sample handling/ processing and sample shipping are provided in the Laboratory Manual in the ISF.

The central laboratory will send reports to the investigator. It is the responsibility of the investigator to evaluate the laboratory reports. Clinically relevant abnormal findings as judged by the investigator will be reported as adverse events (see [Section 5.2.6](#)).

The central laboratory will transfer the results of the analysis to the sponsor.

Clinically relevant abnormal laboratory test results must be confirmed using an unscheduled visit laboratory kit and should be repeated until normalization or stabilization or until an alternative explanation has been found. Abnormal laboratory values will be also graded for intensity by using RCTC Version 2.0 criteria ([R13-3515](#)).

In case the criteria for hepatic injury are fulfilled, a number of additional measures will be performed (see [Section 5.2.6.1](#)) and the DILI Checklist provided in the ISF EDC system. The amount of blood taken from the patient concerned will be increased due to this additional sampling.

Table 5.2.3: 1 Laboratory tests

Category	Test name
Haematology	Hematocrit (Hct) Hemoglobin (Hb) Glycosylated Hbc (HbA1c) (required to be tested at screening and every 48 weeks) Red Blood Cell Count/ Erythrocytes Reticulocyte Count White Blood Cells / Leukocytes Platelet Count/ Thrombocytes
Diff. Automatic	Neutrophils (relative and absolute count) Eosinophils (relative and absolute count) Basophils (relative and absolute count) Monocytes (relative and absolute count) Lymphocytes (relative and absolute count) Neutrophils, bands (Stabs) Neutrophils, polymorphonuclear (PMN) Eosinophils Basophils Monocytes Lymphocytes
Diff. Manual (if Diff Automatic is abnormal)	Activated Partial Thromboplastin Time (aPTT) Prothrombin time (INR) Fibrinogen
Coagulation	AST (GOT) ALT (GPT) Alkaline Phosphatase (AP) Creatine Kinase (CK) CK-MB, only if CK is elevated Gamma-Glutamyl Transferase (GGT/γ-GT) Lactic Dehydrogenase (LDH) Amylase Lipase
Enzymes	Calcium Sodium Potassium Chloride
Electrolytes	

Table 5.2.3: 1 (cont) Laboratory tests

Category	Test name
Substrates	Glucose BUN (blood urea nitrogen) Uric acid Creatinine eGFR (estimated by CKD-EPI formula) (only at screening) Bilirubin Total Bilirubin Direct (if total is elevated) Bilirubin Indirect (if total is elevated) Troponin (Reflex, in case of elevated CK) Protein, Total Albumin C-Reactive Protein (CRP) Cholesterol, total Triglycerides LDL-Cholesterol HDL-Cholesterol IgE ¹ , IgG Hepatitis C Antibodies (qualitative) ⁴ HIV-1, and HIV-2 Antibody (qualitative) ⁴ Hepatitis B Surface Antigen (qualitative) ⁵ Hepatitis B core Antibody ⁵ AntibodyHBV-DNA (quantitative PCR) ^{2,5} QuantiFERON®-TB ^{3,6} Human Chorionic Gonadotropin in urine Human Serum Chorionic Gonadotropin
Specific gamma-globulin quantification	
Infections testing	
TB screening	
Urine Pregnancy test (only female patients of childbearing potential)	
Serum Pregnancy test (only female patients of childbearing potential if urine pregnancy test is positive)	
Hormones (required to be tested at screening and every 48 weeks)	TSH (free T3 and free T4 in case of abnormal TSH result)
Urinalysis (dipstick)	Urine Nitrite Urine Protein Urine Glucose Urine Ketone Urobilinogen Urine Bilirubin Urine RBC/ Erythrocytes Urine WBC/ Leukocytes Urine pH Urine Sediment Bacteria Urine Cast in Sediment Urine Squamous Epithelial Cells Urine Sed. Crys., Unspecified Urine Sediment RBC/ Erythrocytes Urine Sediment WBC/ Leucocytes Albumin (quantitative) Calprotectin
Urine-Sediment (microscopic examination, only if urine analysis abnormal)	
Urine (only at screening)	
Faecal sample	

¹Only in case of allergic reaction

²A HBV-DNA should be conducted if Hepatitis B core Antibody is positive and Hepatitis B surface Antigen is negative.

³If the 1st QuantiFERON®-TB test result is undetermined, a re-test should be performed. If the re-test QuantiFERON-TB test result is undetermined, a PPD skin test should be performed.

⁴HCV and HIV at screening only.

⁵HBV at screening and EOT.

⁶In patients with a previously (i.e. in ongoing extension trial) negative QuantiFERON®-TB test, the test should be repeated every 48 weeks, as long as the results are negative.

Table 5.2.3: 2 Additional testing

Category	Test name
Stool studies to evaluate for enteric pathogens (Faecal assessment for enteric pathogens has to be done V 1 and at suspicion of an disease flare to exclude enteric infection)	Salmonella Shigella Yersinia Campylobacter E. coli Clostridia difficile toxin Enteric parasites and their ova (including Cryptosporidia)

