7.2.5 Safety analyses

Refer to [Section 7.2.2](#) for a description of the analyses of the primary endpoint, which for the present trial is a safety endpoint.

For the additional safety analyses described below, all treated patients will be included. In general, these additional safety analyses will be descriptive in nature and will be based on BI standards. No hypothesis testing is planned.

Statistical analysis and reporting of adverse events will concentrate on treatment-emergent adverse events, i.e. all adverse events occurring between start of treatment in this trial and the end of the REP. Refer to [Section 7.2.2](#) for the complete description of a treatment-emergent adverse event.

Frequency, severity, and causal relationship of adverse events will be tabulated by system organ class and preferred term after coding according to the current version of the Medical Dictionary for Drug Regulatory Activities (MedDRA) at database lock.

Laboratory data will be analysed both quantitatively as well as qualitatively. The latter will be done via comparison of laboratory data to their reference ranges. Values outside the reference range as well as values defined as clinically relevant will be summarised.

Laboratory data will be analysed descriptively with regard to distribution parameters as well as with regard to frequency and percentage of patients with abnormal values or clinically relevant abnormal values.

Vital signs, physical examinations, or other safety-relevant data observed at screening, baseline, during the course of the trial and at the end-of-trial evaluation will be assessed with regard to possible changes compared to findings before start of treatment.

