6.7 BASELINE, TIME WINDOWS AND CALCULATED VISITS

Measurements reported with date and time and taken prior to the start of administration of trial treatment are pre-treatment values. Measurements reported with a date only (and no time) and taken on the day of first administration of trial treatment are assigned as pre-treatment values. These pre-treatment values will be assigned to visits according to the nominal visit number as recorded on the eCRF or as provided by the laboratory.

Refer to Section 5.2 for baseline definitions for each applicable efficacy endpoint in this trial.

For safety endpoints, the baseline is defined as the last value prior to initiation of the maintenance treatment (Visit M1).

Analysis of AE data, concomitant medication or non-drug therapies will not be based on visits. Therefore, no assignment to time windows will be necessary.

Only one observation per time window will be selected for statistical analysis at a particular visit – the value which is closest to the protocol planned visit day will be selected. If there are two observations which have the same difference in days to the planned day, but which are not measured on the same day, the later value will be selected. If there are two observations on the same day, the later value will be selected.

For derivation of the last value on treatment, minimum value on treatment, and maximum value on treatment, all on-treatment values (whether selected in any time window or not; see Table 6.1: 1 for definition of the on-treatment period) will be considered. These will be derived for analysis of laboratory and vital signs data. For identification of potentially clinically significant abnormal laboratory values, all values (whether selected in any time window or not) within the on-treatment period will be considered.

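### SAP 6.7 lets an unscheduled repeat displace the abnormal scheduled sample that prompted it, which can modestly shift by-visit laboratory summaries towards normal

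*Protocol*

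**What the plan says.** Protocol 5.2.3 makes some laboratory sampling depend on the result: "Clinically relevant abnormal laboratory test results must be confirmed using an unscheduled visit laboratory kit and should be repeated until normalization or stabilization". The sentence goes on to allow a third stopping point, when another explanation is found. The same section has clinically relevant abnormal findings reported as adverse events.

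SAP 6.7 sets out how values enter the summaries:

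- **By visit:** one observation per time window, namely "the value which is closest to the protocol planned visit day will be selected". For two observations equally far from the planned day "but which are not measured on the same day, the later value will be selected". For same-day pairs: "If there are two observations on the same day, the later value will be selected".
- **Last, minimum and maximum:** "For derivation of the last value on treatment, minimum value on treatment, and maximum value on treatment, all on-treatment values" are considered, whether or not they were picked for a window.
- **Potentially clinically significant abnormalities:** also identified from every on-treatment value.

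Protocol 7.2.5 plans the laboratory output: "Laboratory data will be analysed descriptively with regard to distribution parameters as well as with regard to frequency and percentage of patients with abnormal values", together with clinically relevant abnormal values.

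**The concern.** Section 5.2.3 prompts a repeat after a clinically relevant abnormal result and none after a normal one. SAP 6.7 then treats scheduled and repeat samples as interchangeable. A repeat prompted by an abnormal value can become the by-visit value in its place, and repeats of this kind will on average lie closer to normal than the result that prompted them.

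The trial is single-arm, so no comparator carries the same shift. By-visit means and any by-visit abnormality percentages would look somewhat better than the scheduled samples alone would show. They could also disagree with the minimum and maximum tables built from the same data.

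The last value on treatment raises a related question of interpretation. After the EOT sample there is normally no further scheduled laboratory sample in the on-treatment period. A later on-treatment value would therefore usually be an unscheduled one.

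**Working it through.** The plan gives no figure for this, so the check applies the SAP 6.7 rule directly.

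**Inputs from the documents**
- Visit window ±7 days (Protocol, Flow Charts 1A and 1B).
- Nearest-day selection, with ties and same-day pairs to the later value (SAP 6.7).
- EOT on day 2353 and EOS on day 2466 (Flow Chart 1C). The on-treatment period ends 112 days after the last dose (SAP Table 6.1: 1).
- Up to 20 patients (Protocol 7.5).

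**Assumptions not in the documents**
- The scheduled sample is equally likely on each of the 15 days d = -7 to +7.
- The repeat comes g days later, and both samples fall in the same analysis window.

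**By-visit displacement.** For g > 0 the repeat is selected if |d + g| ≤ |d|, that is, if d ≤ -g/2. For g = 0 the later sample is always selected.

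| Repeat delay g (days) | Values of d that give displacement | Share |
|---|---|---|
| 0 | all | 15/15 (100%) |
| 1 | -7 to -1 | 7/15 (47%) |
| 3 | -7 to -2 | 6/15 (40%) |
| 5 | -7 to -3 | 5/15 (33%) |
| 7 | -7 to -4 | 4/15 (27%) |
| 10 | -7 to -5 | 3/15 (20%) |
| 14 | -7 only | 1/15 (7%) |
| 15 or more | none | 0/15 |

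Averaged over delays of 1 to 14 days the share is 56/210 (27%). If the scheduled sample is on or after the planned day, a repeat on a later day never displaces it.

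**Two illustrative patients at M4 (planned day 85)**
- 5.0 × ULN on day 80 (distance 5) and 0.9 on day 87 (distance 2): by-visit value 0.9, last of the two 0.9, maximum 5.0.
- 5.0 × ULN on day 86 (distance 1) and 0.9 on day 93 (distance 8): by-visit value 5.0, last of the two 0.9, maximum 5.0.

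The maximum keeps the abnormal value in both cases.

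**Illustration of the effect on a by-visit abnormality rate.** Further assumptions: 10% of scheduled values are abnormal, all of these are repeated, and values are normally distributed with a within-patient correlation of 0.5 or 0.7. The chance that a repeat falls below the threshold is then 0.676 or 0.532.

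Reported rate = 10% × (1 − displacement share × chance that the repeat is normal)

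- Correlation 0.5: 10% × (1 − 0.400 × 0.676) = 7.3% for g = 3; 10% × (1 − 0.267 × 0.676) = 8.2% for g = 7.
- Correlation 0.7: 10% × (1 − 0.400 × 0.532) = 7.9% for g = 3; 10% × (1 − 0.267 × 0.532) = 8.6% for g = 7.

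The shift is 1.4 to 2.7 percentage points. With 20 patients that is 0.28 to 0.54 of a patient per visit.

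**Last value on treatment.** 2466 − 2353 = 113 days, one day past the 112-day limit, and the EOS window in Flow Chart 1C only runs later (+7). For a completer dosed at EOT, the EOS sample is therefore off-treatment. For early stoppers Protocol 3.3.4.1 puts EOS 16 weeks (112 days) after the last dose, so the EOS sample counts as on-treatment only if it falls no later than that day.

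**The case against.** A reader might infer that laboratory abnormalities are selectively removed from the analysis. The documents do not support that. SAP 6.7 itself takes the minimum, the maximum and the potentially clinically significant values from all on-treatment data. Clinically relevant abnormal results become adverse events, which are not analysed by visit, and SAP Section 7 lists every individual value.

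A reader might also infer that the last value on treatment is bound to be normal. It is not: repeats may stop at stabilisation or once another explanation is found, so the final repeat can still be abnormal. A later genuine on-treatment measurement is also what that statistic is meant to report. Restricting it to scheduled samples would hide a repeat that had worsened.

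Four more objections stand:

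- Only clinically relevant abnormalities must be repeated, so the 7.3% to 8.6% illustration, which repeats every abnormal value, rests on invented inputs and probably overstates the shift.
- Displacement by a later-day repeat needs an early scheduled sample. At EOT, Flow Chart 1C allows only +7 days, although Flow Chart 2C allows ±7.
- The selection is not strictly one-way. Protocol 6.2.2 allows unscheduled samples for other safety reasons, and flare and relapse confirmation visits carry safety labs. Any of these could replace a normal scheduled value.
- Protocol 7.2.5 speaks of percentages of patients with abnormal values and does not say that these are by visit.

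Finally, the SAP's laboratory subsection and time-window table, and the laboratory-data standard in its reference list, could not be consulted. A rule preferring the scheduled sample may sit there. The report is also abbreviated, so it is unclear which laboratory tables will be produced.

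None of this removes the central point. The visible rule in SAP 6.7 lets a result-triggered repeat displace the sample that triggered it.

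**Conclusion.** The point holds as a modest weakness in the by-visit laboratory rule. Under uniform visit timing, a repeat 3, 5 or 7 days later displaces the scheduled value in 40%, 33% or 27% of cases. A same-day repeat always does, and a repeat 15 or more days later never does. The likely direction is towards normal. The size in this trial cannot be fixed from the documents, and the illustrative shift is below one patient per visit at the maximum sample size.

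No safety signal is lost overall, and the exposure-adjusted adverse event rate does not depend on visit windows. The last-value definition can stand, but its reader should be told when the value is an unscheduled repeat. All of this is conditional on the unseen laboratory text of the SAP not already preferring the scheduled sample.

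**What to change.** In SAP 6.7, for laboratory data:

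1. By-visit summaries use the scheduled (nominal-visit) sample. An unscheduled or repeat sample in the window is used only if the scheduled one is missing. SAP 6.7 already assigns pre-treatment values by nominal visit, so this extends an existing convention.
2. Minimum, maximum and potentially clinically significant abnormalities continue to use all on-treatment values.
3. The last value on treatment keeps its definition. Either show the last scheduled on-treatment value beside it, or flag patients whose last value is an unscheduled repeat.

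If the laboratory subsection or the time-window table already contains item 1, a cross-reference in 6.7 is enough for that item.

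The cost is one sentence or two, a filter on the unscheduled-visit flag and slightly more programming. No new data are needed. By-visit figures may look slightly less favourable.
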